1. INTRODUCTION

Spinal cord stimulation (SCS) is a well-established treatment for chronic intractable pain. The purpose of this study is to collect confirmatory data to show that the Gemini Spinal Cord Stimulation neuromodulation system functions as intended in a clinical setting.

The clinical investigation will be conducted in accordance with this CIP. All investigators involved in the conduct of the clinical investigation will be qualified by education, training, or experience to perform their tasks, and training will be documented appropriately.

1.1. Background and Rationale

1.1.1. Background

It is estimated that 20.4% (50 million) of US adults suffer from chronic pain and 8% of adults have high-impact chronic pain [1]. The economic burden of chronic pain is high worldwide, with annual costs estimated as high as \$635 billion dollars in the US [2]. Chronic pain has been linked to loss of mobility, opioid dependence, anxiety, and depression, leading to an overall decrease in quality of life [1]. Additionally, up to 15% of all chronic pain patients are unresponsive to standard medical therapy, and therefore, seek alternative options [2]. Considering the long-term detrimental effects of opioid use and its societal impact [3], it is imperative to explore alternative strategies for handling long-term pain management.

SCS is a commonly utilized form of neurostimulation developed by Abbott and other companies over the past four decades to address chronic pain. It is a minimally invasive and reversible procedure in which leads are placed into the epidural space. When an electrical current is applied to the leads, large myelinated fibers of the dorsal column are stimulated, mitigating pain. Abbott is an established manufacturer of neurostimulation systems, including spinal cord stimulators that can deliver tonic stimulation and the BurstDR™ waveform [4-6]. Tonic stimulation delivers impulses at a consistent amplitude, frequency, and pulse width, and typically produces paresthesia over the patient's area of pain. In contrast, BurstDR™ stimulation delivers impulses in rapid succession, known as a burst train, followed by a short silent phase. Programmable parameters include the amplitude of the burst train, the time from onset of one burst train to the onset of the next burst train (burst rate), and the rate of pulses within each train (intra-burst rate). Amplitudes programmed for burst are typically lower than those traditionally used for tonic stimulation, typically resulting in pain suppression without paresthesia.

Abbott has produced both rechargeable and non-rechargeable (primary cell) systems. Primary cell systems contain an implanted battery of sufficient size to power the implant for its expected lifetime and are surgically replaced upon battery depletion. Rechargeable systems utilize a wireless power transfer system to allow patients to recharge the batteries of the implanted system. Rechargeable systems allow for longer useful life of implanted systems, especially in cases where higher power stimulation settings are desired. Rechargeable systems also allow for smaller implanted devices, as the battery does not need to be large enough to support the entire implant lifetime.

The investigational device for this study is the new Gemini rechargeable SCS system, including IPG, charger, and supporting programmer and controller. The investigational system is compatible with Abbott's existing on-market SCS leads, extensions and adapters.

████████████████████ The investigational system also leverages Abbott's iPad clinician programmer app and iPhone patient controller app to provide clinician and patient control of the implanted device.

Clinical Investigation Plan

1.1.2. Rationale for Conducting this Clinical Investigation

The benefits of SCS and BurstDR therapy are well established. The Gemini SCS system introduces a novel IPG, charger, and supporting applications. Extensive testing has been performed to demonstrate safety, functionality, usability, and efficacy of these devices and this study is designed to further support those data with clinical experience. Many facets of the system leverage Abbott's existing on-market technologies such as approved leads, iOS patient controller and clinician programmer applications, patient contacting materials etc., which have been demonstrated as safe through previous testing and field experience. The study focuses on safety events that could be attributed to the new charging system and is designed to detect any serious effects caused by the new component of the system. The study further supports the Gemini SCS system under the European Medical Devices Regulation (EU MDR) which requires the manufacturer to generate sufficient clinical evidence on the device for CE-Mark. This standard is internationally recognized, [REDACTED].

Clinical Investigation Plan

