2. CLINICAL INVESTIGATION OVERVIEW

2.1. Clinical Investigation Objective

2.1.1. Primary Objective

The objective of this study is to collect confirmatory data to show that the Gemini SCS neuromodulation system functions as intended in a clinical setting.

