3. CLINICAL INVESTIGATION DESIGN

This is a pre-market, prospective, single-arm, non-randomized, open-label multi-center clinical study designed to show that the Gemini SCS neurostimulation system functions as intended in a clinical setting.

The study is designed to report on 20 subjects who receive a Gemini SCS implant and complete follow-up. [REDACTED] The clinical investigation will be conducted at up to 8 centers in Australia.

[figure not shown]
The Sponsor has designed this clinical investigation to involve as little pain, discomfort, fear, and any other foreseeable risk as possible for subjects. Refer to the Risks Analysis section of this clinical investigation plan for details.

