3.2. Measures Taken to Avoid and Minimize Bias

An independent Clinical Events Committee (CEC) will adjudicate all serious adverse events, including all deaths, and all non-serious device- and procedure-related adverse events.

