4. ENDPOINTS

4.1. Confirmatory Safety Endpoint

The confirmatory safety endpoint is the rate of serious adverse events adjudicated as related to the investigational IPG and/or charging system. No formal hypothesis test will be evaluated, but data for the endpoint will be used to confirm whether Gemini SCS system functions as intended.

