8.2.1. Confirmatory Safety Endpoint

The confirmatory safety endpoint for this study is the rate of SAEs related to the IPG and/or charging system.

The confirmatory endpoint will be summarized as the number and percentage of subjects with IPG and/or charging system related SAEs, along with exact 95% Clopper-Pearson confidence intervals.

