2.3 Endpoint Analysis

2.3.1 Confirmatory Safety Endpoints

The confirmatory safety endpoint for this study is the rate of Serious Adverse Events (SAEs) related to the IPG and/or charging system.

No formal hypothesis is formulated for this study. The confirmatory endpoint will be summarized as the number and percentage of subjects with IPG and/or charging system related SAEs, along with exact 95% Clopper-Pearson confidence intervals.

The confirmatory endpoint will be analyzed using safety population defined in 2.1. The evaluable subjects will include those who complete their 6-week visit or had IPG and/or charging related SAE at/prior to their termination before 6 weeks visit.

Charging system related SAE(s) will also be analyzed separately using safety population defined in 2.1. The evaluable subjects will include those who complete their 6-week visit or had charging system related SAE at/prior to their termination before 6 weeks visit.

Statistical Analysis Plan

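### Does the rationale's statement that the study will detect any serious effect of the new component need correcting, given only 20 subjects?

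*Protocol*

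**What the plan says.** The rationale in Protocol 1.1.2 says that the study concentrates on safety events attributable to the new charging system and "is designed to detect any serious effects caused by the new component of the system". The same section presents the study as clinical experience added to testing already done.

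The size is given in Protocol 3 and repeated in SAP 1.3: "The study is designed to report on 20 subjects who receive a Gemini SCS implant and complete follow-up". The text after that sentence, and both sample size sections (Protocol 8.3, SAP 2.4), are redacted.

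The sections that govern conduct and analysis read as follows:

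- Protocol 2.1.1 sets the objective: "collect confirmatory data to show that the Gemini SCS neuromodulation system functions as intended".
- Protocol 3.2 provides an independent committee that "will adjudicate all serious adverse events, including all deaths".
- Protocol 4.1 and SAP 1.4.1 rule out a hypothesis test and say that "data for the endpoint will be used to confirm whether Gemini SCS system functions as intended".
- Protocol 8.2.1 and SAP 2.3.1 summarise the number and percentage of subjects with a related serious event "along with exact 95% Clopper-Pearson confidence intervals".
- SAP 2.3.1 defines the denominator: "The evaluable subjects will include those who complete their 6-week visit or had IPG and/or charging related SAE" before an early termination. It adds a second analysis: "Charging system related SAE(s) will also be analyzed separately using safety population defined in 2.1".

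On follow-up, Protocol 5.7 describes roughly 6 weeks after implant. Protocol 6.3.2, the schedule in 6.3.5 and Appendix IX all place the 6-week visit at 30 to 45 days.

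**The concern.** The word *any* has no limit on rate, probability or time in the visible text, and a study of about 20 subjects cannot have that property. A serious effect in one or two patients per hundred would more likely than not go unseen.

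The worry is how a clean result would be read. Protocol 1.1.2 goes on to link the study to the clinical evidence needed for CE marking, and Protocol 4.1 uses the endpoint to confirm that the system works as intended without saying how the result is to be judged. Beside a sentence promising detection of any serious effect, 0/20 could pass for evidence that such effects are absent. The charging-only analysis in SAP 2.3.1 comes closest to the sentence and has the same limit.

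A second point concerns exposure. A subject whose final visit falls on day 30 is under surveillance for less time, and has fewer planned charges, than one seen at six weeks. Both count alike as evaluable.

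**Working it through.** **Inputs.** The visible n is 20 (Protocol 3, SAP 1.3). The unit is a subject with at least one related serious event (Protocol 8.2.1, SAP 2.3.1), so the binomial model applies. No expected event rate is visible, and Protocol 15.2 says the exact frequency of risk is unknown, so the risks below are illustrative. With the sample size sections redacted, there is no figure of the plan's own to reproduce. I assume independent subjects and that every related serious event is reported and adjudicated as related.

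**Chance of at least one affected subject**, 1 − (1 − p)^20:

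- p = 1%: 1 − 0.99^20 = 18.2%
- p = 2%: 1 − 0.98^20 = 33.2%
- p = 5%: 1 − 0.95^20 = 64.2%
- p = 10%: 1 − 0.90^20 = 87.8%

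**Risk needed for a given chance c**, p = 1 − (1 − c)^(1/20):

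- c = 50%: 3.4%
- c = 80%: 7.7%
- c = 90%: 10.9%
- c = 95%: 1 − 0.05^(1/20) = 13.9%

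**Interval the plan would print.** For 0/20 the Clopper-Pearson upper limit is 1 − 0.025^(1/20) = 16.8%. For 1/20 the interval is 0.1% to 24.9%.

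**If the evaluable number is not 20:**

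| n | Risk giving a 95% chance of at least one | Upper limit at 0/n |
|---|---|---|
| 18 | 15.3% | 18.5% |
| 20 | 13.9% | 16.8% |
| 22 | 12.7% | 15.4% |
| 25 | 11.3% | 13.7% |
| 30 | 9.5% | 11.6% |

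A 95% chance of seeing at least one affected subject needs ln(0.05)/ln(1 − p) subjects: about 59 at 5%, 149 at 2% and 299 at 1%. No plausible redacted rationale for a study of about this size would make the literal claim true.

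**Where the sentence enters the plan.** The endpoint definition, evaluable set, interval method, missing-data rule and analysis timing (Protocol 4.1, 8.2.1 and 8.4; SAP 2.3.1, 2.6 and 2.7) neither cite Protocol 1.1.2 nor depend on it. With the sentence deleted, the report would contain the same count, percentage and interval. For the charging-only analysis, SAP 2.3.1 does not repeat the interval. SAP 2.2.2 supplies it for categorical results where applicable, and an analyst would apply it here as in the combined analysis.

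**Follow-up window.** Day 30 is 42 − 30 = 12 days short of six weeks, or 12/42 = 29%. Assume a first charge on day d and weekly charges after it. The planned number by day T is then floor((T − d)/7) + 1. For d = 10 to 14 this gives 3 by day 30 and 5 by day 42. The documents give no distribution of visit days, so no effect on the event rate can be derived. Day 42 lies inside the 30 to 45 day window, and the window is the same wherever it appears.

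**The case for a change.** The strongest case for a change is that the sentence is false as written, the proof takes one line, and the remedy is cheap. A reworded rationale would be more modest and easier to defend. A further sentence in Protocol 4.1 and SAP 1.4.1 could tie the functions-as-intended conclusion to the interval. A phone contact near day 42 would even out surveillance.

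The arithmetic stands, and so does the remark that *any* is too strong for a statement of capability. The proposed changes gain little:

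- **The rationale sentence.** It can equally mean that serious events are captured and adjudicated, and the objective, committee and descriptive analysis all fit that meaning. No operative section uses the power-type reading.
- **The linking sentence.** Protocol 4.1 already says the endpoint data inform the conclusion, and 8.2.1 already defines the endpoint summary to include the interval. Without a threshold, telling readers to read the result against its upper limit adds no rule.
- **The phone contact.** It resolves no contradiction. It would also touch the lost-to-follow-up definition (Protocol 5.5) and the analysis trigger (Protocol 8.4, SAP 2.6), both tied to the 6-week visit. Surveillance would still be unequal whenever a call was missed.

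Misreading of a 0/20 result remains possible, but the report must show the interval beside the count.

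**Conclusion.** No change to the plan follows. Protocol 1.1.2 is loosely worded: with 20 evaluable subjects, a 95% chance of observing an affected subject needs a true risk of about 13.9%, an even chance needs about 3.4%, and 0/20 is compatible with a risk of up to 16.8%. These figures assume independent subjects, complete reporting and adjudication, and an evaluable number near 20. Between 18 and 30 subjects the 95% threshold runs from 15.3% down to 9.5%, so the reading is the same.

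The overstatement is confined to background text. The analysis that produces the result is openly descriptive and carries the exact interval that conveys this uncertainty, so rewording would alter no estimate, denominator or decision. The visit window is an ordinary operational allowance, stated consistently, with no demonstrable effect on the endpoint. This judgement concerns the visible text only and assumes nothing about the redacted sections.

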2. CLINICAL INVESTIGATION OVERVIEW

2.1. Clinical Investigation Objective

2.1.1. Primary Objective

The objective of this study is to collect confirmatory data to show that the Gemini SCS neuromodulation system functions as intended in a clinical setting.

2.2. Devices Used in the Clinical Investigation

2.2.1. Name of the Devices Under Investigation

The following investigational components of the Gemini SCS neuromodulation system will be used in this clinical investigation:

Device name	Model	Manufacturer	Region	Investigational or Market Released
Gemini SCS IPG	32400	Abbott	Australia, Europe	Investigational
Gemini Wireless Charger	16000			
Gemini Clinician Programmer App	55600			
Gemini Patient Controller App	55500			
IPG Pocket Sizer	12720			
IPG Port Plug	12710			
Charger AC Adapter	16720			
Charging Apparel, SCS (reusable)	16750			
Gemini Charging Cable	16710			

These investigational components are used with on-market leads and accessories (CL1014851).

2.2.2. Indication for Use

This neurostimulation system is indicated as an aid in the management of chronic, intractable pain of the trunk and/or limbs, including unilateral or bilateral pain associated with the following:

Clinical Investigation Plan

failed back surgery syndrome, intractable low back and leg pain, angina pectoris and peripheral vascular disease.

2.2.3. Description of the Devices Under Investigation

The Gemini SCS IPG is a 16-channel, rechargeable electronic device designed to be connected to one or more leads with up to 16 total electrodes. The IPG is powered by a hermetically sealed rechargeable battery within a titanium case and uses microelectronic circuitry to generate constant-current electrical stimulation to nerve structures. A wireless charger placed over the IPG recharges the battery of the implanted device. The IPG and wireless charger communicate via Bluetooth with an external programmer and a patient control device. The external programmer enables the clinicians to adjust and fine-tune the low intensity pulses of current that stimulate the nerve structures. Patients are provided with a controller to further control and assess the status of the system.

Additional information and details on the components of the Gemini rechargeable SCS system are available in the Investigator Brochure.

2.2.4. Summary of Preclinical Studies

The Gemini Investigator Brochure contains details of bench testing and preclinical studies conducted with the Gemini rechargeable SCS system.

3. CLINICAL INVESTIGATION DESIGN

This is a pre-market, prospective, single-arm, non-randomized, open-label multi-center clinical study designed to show that the Gemini SCS neurostimulation system functions as intended in a clinical setting.

The study is designed to report on 20 subjects who receive a Gemini SCS implant and complete follow-up. [REDACTED] The clinical investigation will be conducted at up to 8 centers in Australia.

[figure not shown]
The Sponsor has designed this clinical investigation to involve as little pain, discomfort, fear, and any other foreseeable risk as possible for subjects. Refer to the Risks Analysis section of this clinical investigation plan for details.

3.1. Clinical Investigation Procedures and Follow-up Schedule

The flowchart and the follow-up requirements of this clinical investigation are described below. Enrollment, baseline and permanent implant can occur on the same day.

Clinical Investigation Plan

Figure 1: Clinical Investigation Flowchart

Clinical Investigation Plan

3.2. Measures Taken to Avoid and Minimize Bias

An independent Clinical Events Committee (CEC) will adjudicate all serious adverse events, including all deaths, and all non-serious device- and procedure-related adverse events.

3.3. Suspension or Early Termination of the Clinical Investigation

While no formal statistical rule for early termination of the clinical investigation for insufficient effectiveness of the device under investigation is defined, the Sponsor reserves the right to discontinue the clinical investigation at any stage or reduce the follow-up period with suitable written notice to the investigator. Possible reason(s) may include, but are not limited to:

- Unanticipated adverse device effect (e.g., UADE) occurs and it presents an unreasonable risk to the participating subjects
- Further product development is cancelled

If the Sponsor discontinues the clinical investigation, sites will follow subjects per routine hospital practice with device-related AEs reported to the Sponsor as per vigilance/commercial reporting requirements. The investigator shall return all clinical investigation materials (including devices that are not currently implanted) to the Sponsor and provide a written statement to the EC (if applicable). All applicable clinical investigation documents shall be subject to the same retention policy as detailed in Section 11.5 of the CIP.

If the Sponsor suspends or prematurely terminates the clinical investigation at an individual site in the interest of safety, the Sponsor will inform all other Principal Investigators.

If suspension or premature termination occurs, the Sponsor will remain responsible for providing resources to fulfill the obligations from the CIP and existing agreements for following the subjects enrolled in the clinical investigation, and the Principal Investigator or authorized designee will promptly inform the enrolled subjects at his/her site, if appropriate.

A Principal Investigator, EC, or regulatory authority may also suspend or prematurely terminate participation in the clinical investigation at the investigational site for which they are responsible. The investigators will follow the requirements specified in the Clinical Trial Agreement.

If a suspended investigation is to be resumed, a prior approval should be obtained from the EC and a notification should be sent to the regulatory bodies.

4. ENDPOINTS

4.1. Confirmatory Safety Endpoint

The confirmatory safety endpoint is the rate of serious adverse events adjudicated as related to the investigational IPG and/or charging system. No formal hypothesis test will be evaluated, but data for the endpoint will be used to confirm whether Gemini SCS system functions as intended.

4.2. Additional Endpoints

Additional endpoints are reported using descriptive statistics, without hypothesis testing:

Clinical Investigation Plan

- All serious adverse events
- Non-serious adverse events related to device, procedure, stimulation, charging, or MRI (investigational device and on-market devices)

Additional data collected:

- Patient satisfaction
- Patient experience with charging
- NRS score change
- PROMIS-29 change
- Charging history
- Stimulation programs used
- Stimulation programs available

5. SUBJECT SELECTION AND WITHDRAWAL

5.1. Subject Population

This clinical investigation will enroll subjects scheduled to receive a Gemini SCS implant for an approved chronic pain indication. Patients must meet all general eligibility criteria and provide written informed consent prior to sites conducting any investigation-specific procedures not considered standard of care.

5.2. Subject Recruitment/Screening and Informed Consent

5.2.1. Subject Recruitment and Screening

A member of the site's clinical investigation team previously trained to the CIP must evaluate patients for the general clinical investigation eligibility criteria, and if applicable, will enter the patients into a site-specific screening log. A patient who does not satisfy all general eligibility criteria prior to informed consent is considered a screen failure and should not be enrolled in the clinical investigation.

Sites will ask patients meeting all inclusion criteria and no exclusion criteria to sign an Informed Consent form following the established Informed Consent process (described in Section 5.2.2) to participate in the clinical investigation. Sites will enter these patients into the screening log. Once a duly dated and signed Informed Consent form is obtained, the clinical investigation-specific procedures may begin.

5.2.2. Informed Consent

The Investigator or an authorized designee (if applicable) will conduct the Informed Consent process, as required by applicable regulations and the center's EC. This process will include a verbal discussion with the patient on all aspects of the clinical investigation that are relevant to the patient's decision to participate, such as details of clinical investigation procedures,

Clinical Investigation Plan

anticipated benefits, and potential risks of clinical investigation participation. Sites must inform patients about the right to withdraw from the clinical investigation at any time and for any reason without sanction, penalty, or loss of benefits to which the patient is otherwise entitled. Withdrawal from the clinical investigation will not jeopardize future medical care or relationship with the investigator.

During the discussion, the Principal Investigator or an authorized designee will avoid any improper influence on the patient and will respect patient's legal rights. Financial incentives will not be given to patients. Patients may be compensated for time and travel directly related to the participation in the clinical investigation. The site shall provide the patient with the Informed Consent form written in a language that is understandable to the patient and that has been approved by the center's EC. The patient shall have adequate time to review, ask questions, and consider participation. The Principal Investigator or an authorized designee will make efforts to ensure that the patient understands the information provided. If the patient agrees to participate, the patient must sign and date the Informed Consent form, along with the person obtaining the consent prior to any clinical investigation-specific procedures. The site will file the signed original in the patient's hospital or research charts and provide a copy to the patient. All serious adverse events and any device-related adverse events as defined in Section 7.1 are reportable once a subject has signed and dated the ICF.

Sites will report any failure to obtain informed consent from a patient to the Sponsor within 5 working days and to the reviewing center's EC according to the EC's reporting requirements.

If, during the clinical investigation, new information becomes available that can significantly affect a subject's future health and medical care, the Principal Investigator or authorized designee (if applicable) will provide this information to the subject. If relevant, sites will ask the subject to confirm their continuing informed consent in writing.

